4.3 Efficacy Parameters

4.3.1 Clinical efficacy indices

- **Recovery of gastrointestinal motility** including time to first postoperative passage of flatus (recorded to the exact hour and minute), time to first postoperative bowel movement (recorded precisely), and restoration of bowel sounds.
- **Incidence of postoperative gastrointestinal dysfunction** related complications: including abdominal distension or pain, nausea, vomiting, and diarrhea.

All the above parameters were observed starting on the day of surgery and continued to be

recorded daily until the fifth postoperative day or discharge, whichever came first.

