2.2 Background

Postoperative gastrointestinal dysfunction (POGD), commonly referred to as postoperative ileus (POI), is a well-recognized complication¹。 Contemporary studies indicate that POI typically persists for 3–5 days and is characterized by transient impairment of gastrointestinal tract (GIT) function following abdominal surgery. Its pathological manifestations primarily involve mucosal injury, disruption of barrier integrity, and impaired gastrointestinal motility. Clinically, patients may present with a wide spectrum of symptoms, including nausea, vomiting, abdominal pain, diarrhea, defecatory difficulties, and diminished or absent bowel sounds^{2,3}.

The pathogenesis of this condition is multifactorial, encompassing surgical techniques and manipulation, disturbances of internal homeostasis, alterations in blood perfusion, anesthetic and analgesic regimens, inflammatory responses, and neuroendocrine mechanisms. In addition, unique physiological characteristics in gynecologic patients, unfavorable psychological states, and surgical positioning further elevate the risk of POGD, underscoring the critical importance of prevention and management⁴⁻¹¹。 Current Western medical approaches comprise supportive measures (such as enemas and fluid replacement), pharmacotherapy (e.g., metoclopramide hydrochloride, mosapride), endoscopic interventions, gastrointestinal pacing devices, and surgical

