2.4.2.5 Dropout Criteria

- (1) Patients who develop subcutaneous hematoma, skin damage, or rash at the primary acupoint sites during the trial, rendering acupuncture infeasible;
- (2) Patients who fail to comply with the prescribed treatment protocol or have incomplete data.

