2.4.2.7 Criteria for Termination of Participation

- (1) Patients experiencing moderate to severe adverse reactions to acupuncture (e.g., needle syncope), or those unwilling to continue treatment;
- (2) Patients who develop serious adverse events or complications that preclude continuation of the study;
- (3) Patients who present with severe gastrointestinal dysfunction during the trial requiring alternative therapeutic interventions.

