2.4.4 Sample Size

This study was designed as a randomized controlled trial, with the treatment group receiving abdominal acupuncture and the control group receiving conventional therapy. The primary outcome measure was the time to first postoperative flatus. Based on published literature, the mean \pm standard deviation of the time to first flatus in the control group was 37.60 ± 4.11

hours. It was anticipated that abdominal acupuncture would reduce this time by approximately

8.1 hours. Assuming a two-sided $\alpha = 0.05$ and a statistical power of 90%, the sample size was

$$n = \frac{2(z_\alpha + z_\beta)^2 * \sigma^2}{\delta^2}$$

calculated using the standard formula:

The required sample size was determined to be 33 participants per group. With a 1:1 randomization ratio, both the abdominal acupuncture group and the control group required 33 participants each. Allowing for a potential 15% dropout or loss to follow-up, the minimum enrollment target was set at 38 participants per group, resulting in a total sample size of no fewer than 76 participants.

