3.1 Basic treatment

The standardized postoperative management protocol consists of the following components:

- (1) Early oral intake: patients may commence a liquid diet 6 hours after surgery, advance to a semi-liquid diet following the passage of flatus, and transition to a regular diet after bowel movement.
- (2) Early mobilization: patients are encouraged to turn in bed and initiate physical activity as early as 6 hours postoperatively, and to ambulate as soon as their condition permits.
- (3) Adequate fluid supplementation.
- (4) Maintenance of fluid–electrolyte and acid–base balance.
- (5) Prophylactic antibiotic therapy to prevent infection.
- (6) Early removal of urinary catheters, drainage tubes, and other indwelling devices.
- (7) Postoperative analgesia: implementation of a multimodal pain management strategy.
- (8) In critically ill patients, supplemental oxygen and continuous electrocardiographic monitoring are required.

Note: During routine management, any interventions potentially impairing gastrointestinal function—such as prokinetic agents, enemas, or traditional herbal therapies—are strictly contraindicated.

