4.1 General Parameters

Collected variables included age, body mass index (BMI), intraoperative blood loss, operative duration, and length of postoperative hospitalization.

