4.3.3 Relevant Assessment Scales

- **Pain assessment:** The Visual analogue scale (VAS) was applied (Appendix 1). Abdominal pain scores were recorded before and after treatment on the day of surgery (5 days after surgery).
- **Gastrointestinal symptom assessment:** Symptom scoring was based on the Perioperative Clinical Evaluation Standards for Gastrointestinal Motility (Guangdong Provincial Standard, Appendix 2). Scores were documented daily from the day of surgery (before treatment) through postoperative Days 1–5, according to observed gastrointestinal function.
- **Quality of life assessment:** The Gastrointestinal Quality of Life Index (GIQLI) was employed (Appendix 3). Assessments were performed on the day of surgery prior to treatment, on postoperative Day 5, and again on Day 14 following the final treatment session.

5. Adverse Events and Management

If adverse reactions occurred during the trial—such as needle stagnation, syncope, breakage, hematoma, or infection—investigators promptly managed the event, ensured patient safety, reassured the participant with an explanation, and documented the details in the case report form.

6. Ethical Principle

This clinical trial was reviewed and approved by the Ethics Committee of Guangdong Provincial Hospital of Traditional Chinese Medicine prior to participant enrollment (Approval No. YF-2023-435-01). The study was conducted in full compliance with the principles of the Declaration of Helsinki.

7. Statistical Analysis

Data were organized and managed using Microsoft Excel to establish a primary database, which was subsequently converted into an SPSS 26.0 database for statistical analysis. The Shapiro–Wilk test was employed to assess the normality of continuous variables. According to data distribution, descriptive statistics were presented as mean \pm standard deviation (SD) for normally distributed variables, and as median with interquartile range [P₂₅, P₇₅] for non-normally distributed variables. Between-group comparisons of normally distributed data were performed using independent-samples t tests, while within-group pre- and post-treatment comparisons were conducted using paired t tests. For non-normally distributed data, the Mann–Whitney U test was applied for between-group comparisons, and the Wilcoxon signed-rank test for within-group comparisons.

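### Time to first bowel movement can be right-censored at Day 5 or discharge, but the stated t-test or Mann-Whitney has no rule for a patient without the event

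*Protocol*

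**What the plan says.** Section 4.3.1 lists time to first flatus and time to first bowel movement, both timed exactly. It states that all indices in that section are "recorded daily until the fifth postoperative day or discharge, whichever came first". Section 2.4.4 names flatus as the primary outcome. Bowel movement is therefore not primary, although the protocol gives it no other label.

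Section 7 checks continuous variables with Shapiro-Wilk. It then says "Between-group comparisons of normally distributed data were performed using independent-samples t tests", with Mann-Whitney U for non-normal data. The only other between-group methods are chi-square or Fisher's exact test and repeated-measures ANOVA. No time-to-event method appears, and no rank or value is assigned to a patient who has not had the event.

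Four other places bear on the point:
- Section 2.4.2.5 treats as dropouts "Patients who fail to comply with the prescribed treatment protocol or have incomplete data".
- Section 2.4.2.7 ends participation for "Patients who present with severe gastrointestinal dysfunction during the trial requiring alternative therapeutic interventions".
- Section 2.2 says "POI typically persists for 3–5 days".
- Section 4.1 collects "length of postoperative hospitalization".

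**The concern.** For a patient without a bowel movement at the cut-off, all that is known is that the time exceeds the cut-off. Because discharge can come before Day 5, that cut-off may differ between patients. The protocol fixes both the window and the tests, and the two do not fit together.

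The easy way out is to analyse only the patients with a recorded time. Those removed are then mostly the slowest, and more of them come from the slower arm. The estimated benefit shrinks and power is lost. If one arm also goes home earlier, the trimming is unequal even when the treatment does nothing, and a false difference can appear.

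Discharge and stopping may themselves be linked to bowel recovery. Diet moves on with it ("transition to a regular diet after bowel movement", section 3.1), and severe gastrointestinal dysfunction ends participation.

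**Working it through.** **Inputs from the protocol.** Window to Day 5 or discharge (4.3.1); tests (7); 33 per group, two-sided 5% (2.4.4, 7); flatus in controls 37.60 h, SD 4.11 h (2.4.4). There is no figure for bowel movement to reproduce. The stated 33 is used as it stands. It does not follow from its own inputs: 2(1.960 + 1.282)² × 4.11² / 8.1² = 5.41, so 6 per group. That is a separate matter and does not affect this point.

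**Step 1: flatus.** The protocol gives "time to first flatus in the control group was 37.60 ± 4.11" hours. Under normality:
- P(T > 48 h) = 1 − Φ((48 − 37.60)/4.11) = 1 − Φ(2.53) = 0.6%.
- P(T > 72 h) = 1 − Φ(8.37) = 3 × 10⁻¹⁷.

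Censoring of the primary outcome is negligible unless patients leave by about 48 h.

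**Step 2: bowel movement, assumed distribution.** Log-normal times; control median m of 48 to 84 h; log-SD s of 0.3 or 0.5; acupuncture median 0.8m; common window c = 120 h.
- Share without a time: 1 − Φ(ln(c/m)/s).
- Mean of all times: m·exp(s²/2).
- Mean of observed times: m·exp(s²/2) · Φ(ln(c/m)/s − s) / Φ(ln(c/m)/s).

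Example, m = 84, s = 0.5. Controls: ln(120/84)/0.5 = 0.713, so 23.8% lack a time. Acupuncture (median 67.2 h): 1.160, so 12.3%. True means are 95.2 and 76.2 h, a difference of 19.0 h. Observed means are 73.0 and 64.7 h, a difference of 8.3 h, or 57% smaller.

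**Step 3: power.** 3,000 simulated trials per row, 33 per arm. CC is complete-case, MW is Mann-Whitney, and worst-rank ties event-free patients at the slowest rank.

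| s | m (h) | No time, control / acupuncture | Mean difference, true → CC (h) | Power: CC MW | Log-rank | Worst-rank MW |
|---|---|---|---|---|---|---|
| 0.3 | 48 | 0.1% / 0.0% | 10.0 → 10.0 | 84% | 79% | 84% |
| 0.3 | 60 | 1.0% / 0.1% | 12.6 → 11.9 | 81% | 78% | 82% |
| 0.3 | 72 | 4.4% / 0.7% | 15.1 → 12.8 | 78% | 78% | 83% |
| 0.3 | 84 | 11.7% / 2.7% | 17.6 → 12.4 | 69% | 78% | 82% |
| 0.5 | 48 | 3.3% / 1.1% | 10.9 → 8.8 | 38% | 39% | 42% |
| 0.5 | 60 | 8.3% / 3.3% | 13.6 → 9.1 | 33% | 38% | 42% |
| 0.5 | 72 | 15.3% / 7.1% | 16.3 → 8.8 | 27% | 39% | 41% |
| 0.5 | 84 | 23.8% / 12.3% | 19.0 → 8.3 | 23% | 38% | 39% |

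If Day 5 is read as 144 h, medians of 60 to 84 h give 0.2% to 14% of controls without a time and a shrinkage of 1% to 44%.

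**Step 4: type I error (no true effect).**
- Same window in both arms: 4.4% to 5.6% for every method.
- One arm cut off 24 h earlier (96 against 120 h), median 84 h: complete-case tests about 22% to 36%, log-rank 5% to 6%, worst-rank 7% to 8%.
- Same shift, median 60 h, s = 0.5: complete-case Mann-Whitney 10%, t-test 13%, log-rank 6%.
- Same shift, medians 48 to 60 h, s = 0.3: all near 5% (4% to 7%).

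**Step 5: discharge or stopping linked to recovery.** Log-SD 0.5, medians 60/72/84 h; true median differences 12.0/14.4/16.8 h.
- Some patients with true times up to 100 h leave early (30% at 72 h, 30% at 96 h): Kaplan-Meier gives 12.1/14.6/19.8 h and complete-case 9.0/9.2/8.7 h. Power is 38/39/36% for log-rank and 39/41/36% for worst-rank.
- Half of those beyond 120 h are stopped at 48 h: Kaplan-Meier gives 11.2/12.6/13.4 h and complete-case 9.9/10.3/10.0 h.

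Kaplan-Meier is nearer the truth than complete-case throughout, but it is not free of bias.

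**The case against.** **The gap is one missing sentence.** Mann-Whitney works once event-free patients are given a rank, and a statistical analysis plan could supply that. This stands in part. But the t-test branch cannot be repaired that way, and it is the protocol that sets the tests against a truncated window.

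**Exclusion is not stated.** Correct. A reader might infer from the dropout criterion on incomplete data that event-free patients are removed. That is plausible, but the protocol does not say it, and the losses above apply only if it is done.

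**Most patients may stay to Day 5.** Sessions run to Day 4 (3.2.5), and laboratory tests, symptom scores and quality of life are due on Day 5 (4.2, 4.3.2, 4.3.3). This stands: the window may be nearly common and few times missing. Allowing discharge as a cut-off still permits earlier exit.

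**The size has no anchor.** This stands. A reader might take the 3 to 5 days in the Background as showing heavy censoring. That figure describes how long ileus lasts, not when bowel movements occur in this population.

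**Log-rank is not shown to be better.** This stands. Worst-rank Mann-Whitney has slightly higher power in every row of the table, and log-rank assumes that discharge and stopping are unrelated to recovery. Worst-rank in turn assumes event-free patients are the slowest, which early discharge can break. The choice of main method is open.

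**Conclusion.** The mismatch is real and confined to time to first bowel movement: a window that can censor, and tests with no provision for a censored patient. Its size cannot be fixed from the protocol. Under the assumed log-normal times and a 120 h window, 0.1% to 24% of controls lack a time, and leaving them out shrinks the mean difference by between 1% and 57%. The harm is small when recovery is quick or uniform and large only when it is slow and spread out.

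Two stronger readings are not supported. One is that the primary result is compromised: on the protocol's own flatus figures the effect is negligible. The other is that false positives are generally inflated: that needs discharge times that differ by arm together with enough slow recoveries, and the protocol does not say that discharge differs. The opposite claim, that type I error is always safe, fails for the same reason.

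This is worth correcting, with medium confidence, and is not critical to the trial's main conclusion.

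**What to change.** For time to first bowel movement only:

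1. Drop the Shapiro-Wilk choice and the t-test, and keep every randomised patient.
2. Use one of these as the main analysis and the other as sensitivity analysis, named in advance: (a) Mann-Whitney with event-free patients, including those stopped for severe gastrointestinal dysfunction, tied at the slowest rank; or (b) Kaplan-Meier with a log-rank test, censored at Day 5 or discharge. Each covers the assumption on which the other depends.
3. Report the number without the event by arm and by reason.

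Leave the primary flatus test unchanged.

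**Cost.** Analysis wording only, plus the discharge time if length of stay is held only in whole days. The effect is no longer expressed as a mean difference in hours. Under a common 120 h window, log-rank gives up about 1 to 5 points of power against worst-rank. When almost no one lacks a time (medians 48 to 60 h, log-SD 0.3), it is also 3 to 5 points below the complete-case test.

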3.2.5 Treatment Course

The first abdominal acupuncture session was performed 4–6 hours postoperatively. From postoperative Day 1 through Day 4, one session was administered daily, with a total of five sessions constituting a complete treatment course. Clinical condition was carefully documented and evaluated throughout and following the treatment period.

4. Outcome Measurements

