Categorical variables were expressed as frequencies (n) and percentages (%), with between-group comparisons analyzed using the chi-square test or Fisher's exact test, as appropriate. Repeated measures analysis of variance (ANOVA) was applied for comparisons across multiple time points between groups. All statistical analyses were two-tailed, and a P value of less than 0.05 was considered statistically significant.

8. References

2. Boeckxstaens GE, de Jonge WJ. Neuroimmune mechanisms in postoperative ileus. *Gut*. 2009;58(9):1300-1311. doi:10.1136/gut.2008.169250
4. Mythen MGM. Postoperative gastrointestinal tract dysfunction: an overview of causes and management strategies. *Cleve Clin J Med*. 2009;76 Suppl 4:S66-71. doi:10.3949/ccjm.76.s4.11
5. Kehlet H. Surgical Stress Response: Does Endoscopic Surgery Confer an Advantage? *World J Surg*. 1999;23(8):801-807. doi:10.1007/s002689900583

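### Protocol 4.3.1 stops recording complications and first bowel movement at discharge, while 4.3.3 scores the same events to Day 5, so incidence can mix observation time with effect

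*Protocol*

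**What the plan says.** **Recording rule.** Protocol 4.3.1 lists first flatus, first bowel movement, bowel sounds, and dysfunction-"related complications: including abdominal distension or pain, nausea, vomiting, and diarrhea". All are followed from the day of surgery and "recorded daily until the fifth postoperative day or discharge, whichever came first".

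**Other schedules.** For the gastrointestinal symptom score, 4.3.3 says: "Scores were documented daily from the day of surgery (before treatment) through postoperative Days 1–5". The form in Appendix 2 covers flatus and defecation (with times), distension or pain, bowel sounds, nausea, vomiting and diarrhoea. Safety tests (4.2), inflammatory markers (4.3.2) and GIQLI (4.3.3) also fall on postoperative Day 5. None of these has a discharge clause or is limited to one arm.

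**Discharge.** No discharge time or criterion is given. Section 4.1 lists "operative duration, and length of postoperative hospitalization" among the variables collected.

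**Treatment schedule.** For the acupuncture arm only, 3.2.5 says: "From postoperative Day 1 through Day 4, one session was administered daily".

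**Tests.** Section 7 has categorical "comparisons analyzed using the chi-square test", with Fisher's exact test as the alternative. For continuous outcomes: "Between-group comparisons of normally distributed data were performed using independent-samples t tests", with the Mann-Whitney U test for non-normal data.

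**The concern.** Under 4.3.1 each patient has her own observation window. One who leaves on Day 3 has fewer days on which nausea, vomiting, distension or diarrhoea can be noted than one who stays to Day 5. The named tests count patients with and without an event and take no account of days observed.

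This would not matter if windows were alike in the two arms, but the protocol does not secure that. Two features could pull them apart, in opposite directions:

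- Sessions through Day 4 give acupuncture patients a reason to stay that controls lack.
- Section 3.1 ties diet to flatus and bowel movement. If acupuncture speeds recovery as the trial hypothesises, treated patients may be ready to leave sooner.

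An incidence difference could then appear, or be hidden, through observation time alone. A first bowel movement after discharge would have no recorded time under 4.3.1. This is a data-collection rule, so an analysis plan cannot restore days that were never recorded.

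**Working it through.** **1. The text.** Sections 4.3.1 and 4.3.3 give two windows for largely the same events. If patients stay or are contacted through Day 5, the discharge clause in 4.3.1 serves no purpose. If they are not, the daily score in 4.3.3 cannot be completed as written. The two sections must be reconciled whatever the size of any bias.

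**2. No plan figure to reproduce.** The protocol states no complication rate, discharge time or power for the incidence endpoint. The only input taken from it is the enrolment target of 38 per group (2.4.4). Daily risks and window lengths below are assumptions.

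**3. Model.** Both arms have the same daily risk *h* of a first complication, so there is no true effect. Apparent incidence after *d* observed days is 1 − (1 − *h*)^*d*. For example, at *h* = 0.10:

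- 5 days: 1 − 0.90^5 = 0.410
- 3 days: 1 − 0.90^3 = 0.271

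False rejection is the exact probability, over two independent binomials with n = 38, that |i − j|/n divided by √[p̄(1 − p̄)·2/n] exceeds 1.96 (uncorrected chi-square). Here i and j are the event counts and p̄ = (i + j)/(2n). Every patient in an arm is given the same window.

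**4. Constant daily risk.**

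| Daily risk | Days observed | Apparent incidence | False rejection |
|---|---|---|---|
| 5% | 5 v 5 | 22.6% v 22.6% | 5.0% |
| 5% | 5 v 4 | 22.6% v 18.5% | 7.2% |
| 5% | 5 v 3 | 22.6% v 14.3% | 15.5% |
| 10% | 5 v 5 | 41.0% v 41.0% | 4.9% |
| 10% | 5 v 4 | 41.0% v 34.4% | 8.9% |
| 10% | 5 v 3 | 41.0% v 27.1% | 24.7% |
| 20% | 5 v 5 | 67.2% v 67.2% | 5.1% |
| 20% | 5 v 4 | 67.2% v 59.0% | 11.2% |
| 20% | 5 v 3 | 67.2% v 48.8% | 36.9% |

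**5. Front-loaded risk.** Here most first events come early.

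| Risk on successive days | Days observed | Apparent incidence | False rejection |
|---|---|---|---|
| 30, 15, 8, 4, 2% | 5 v 3 | 48.5% v 45.3% | 5.9% |
| 20, 10, 5, 3, 2% | 5 v 3 | 35.0% v 31.6% | 6.2% |

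For 5 v 2 days the figures are 10.7% and 10.2%. The shape of the risk over time therefore matters as much as its level.

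**6. First flatus.** On the planning figures in 2.4.4, control mean plus three SDs is 37.60 + 3 × 4.11 = 49.93 h, just past two days after surgery. Loss of this endpoint to early discharge should be uncommon. The protocol gives no comparable figure for first bowel movement.

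Fisher's exact test was not computed. It uses the same counts and likewise ignores days observed.

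**The case against.** The strongest reply is that the rest of the schedule points to observation through Day 5. Bloods, ECG, GIQLI and the daily score are all due then in both arms, and acupuncture runs to Day 4. If patients stay or return as scheduled, windows barely differ. The daily Appendix 2 score also already captures the events. This stands as a reason why the bias may be small. It does not remove the conflict, because 4.3.1 still defines its own endpoints with a discharge cut-off.

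Constant risk is also doubtful. The diagnostic criteria in 2.4.2.2 look to the first 24 hours, and if recovered patients leave first, the days lost carry less risk. That stands too, and is why the front-loaded results are given equal weight.

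A reader might infer more than the text supports:

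- **That the plan makes discharge depend on arm.** It does not say so. There are no discharge rules or times, and the two mechanisms oppose each other and may partly cancel.
- **That an artefact of many percentage points is to be expected.** Such figures need constant risk and a two-day gap between whole arms. Neither is in the protocol.
- **That the primary outcome is compromised.** The planning figures suggest that flatus usually precedes discharge.
- **That early leavers count as fully observed, or drop out of the repeated measures ANOVA.** Section 7 states neither, and handling of missing data may lie in an analysis plan not shown here.

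**Conclusion.** The point holds as an inconsistency about the observation window that can bias a secondary comparison. It affects complication incidence and, to an extent that cannot be sized, time to first bowel movement.

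Neither size nor direction can be fixed from the protocol. With 38 per arm and no true effect, excess false rejection runs from none (all observed to Day 5), through about 6% against a nominal 5% (front-loaded risk, 5 v 3 days), to 16% to 37% (constant daily risk of 5% to 20%, 5 v 3 days). A one-day gap under constant risk gives 7% to 11%. All these figures rest on assumed risks and on one window per arm. The correction is worth making because it is cheap and resolves the contradiction whichever case applies.

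**What to change.** Delete the discharge clause from 4.3.1. Define complication incidence and first bowel movement over one fixed Day 0-5 window for every patient, taken from the daily Appendix 2 score that 4.3.3 already requires. Collect any days after discharge at the Day 5 assessment already scheduled, so that 4.2, 4.3.1, 4.3.2 and 4.3.3 share one schedule. The cost is a wording change and a few questions at an existing contact. The downside is that post-discharge days rest on self-report.

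Section 2.4.2.1 gives enrolment as December 2023 to December 2024, so collection may be over. If post-discharge data do not exist, report observed days by arm. As a sensitivity analysis, also compare incidence over a short fixed window chosen without reference to outcome, for example Day 0-2, and state how many patients in each arm left before it closed. This costs one table and one extra comparison, and it gives up later events.
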